### **10.5.2 Karolinska Sleepiness Scale**

The Karolinska Sleepiness Scale (KSS) is a 9-point scale. The scale has a range from 1 being ‘very alert’ to 9 being ‘very sleepy, great effort to keep awake, fighting sleep’.

Absolute change from baseline (mean of the two PSG morning assessments at V2, run-in period) to Days 1 and 2 (mean of the two PSG morning assessments for a given treatment period) in KSS will be summarized by gender and overall. Absolute values will also be summarized.

### **10.5.3 Sheehan Disability Scale**

Sheehan Disability Scale® (SDS) consists of three questions on impairment of work, social life, and family life/home responsibilities each on a 10-point scale. The three items will be summed into a single dimensional measure of global functional impairment that ranges from 0 (unimpaired) to 30 (highly impaired).

Absolute change from baseline (mean of the two PSG morning assessments at V2, run-in period) to Days 1 and 2 (mean of the two PSG morning assessments for a given treatment period) in SDS will be summarized by gender and overall. Absolute values will also be summarized.

### **10.5.4 Neurological Examination**

The number (%) of subjects answering ‘Yes’ to the question ‘Is excessive sleepiness observed one hour after lights on?’ on the ‘Neurological Examinations’ page will be tabulated for each scheduled PSG morning by dose group (including single-blind placebo) by gender and overall.

The time from treatment until the subject is considered safe to leave the center the next day will be summarized for each scheduled PSG morning by dose group (including single-blind placebo) by gender and overall.

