1.3 Purpose and rationale of the study

1.3.1 Purpose of the study

The main purpose of this dose-response study is to define the ACT-541468 dose(s) that will show a favorable efficacy and safety profile and to assess the safety and tolerability of the compound in elderly subjects with insomnia disorder.

The dose to be studied in future clinical trials will be established based on the change in objectively assessed WASO and safety data, such as next-day residual effect from baseline versus placebo.

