5.1.2.2 Double-blind treatment phase

During the double-blind treatment phase (i.e., at V3, V4, V5, V6 and V7), ACT-541468 and/or ACT-541468-matching placebo will be taken approximately 30 minutes before lights off (= habitual bedtime \pm 5 minutes) in the evening of each of the PSG nights, as shown in [Table 2](#).

Table 2 **Number of capsules taken according to treatment dose**

Treatment dose (mg) \ Dose strength (mg)	Placebo (0)	5	10	25
Placebo (0)	2	0	0	0
5	1	1	0	0
10	1	0	1	0
25	1	0	0	1
50	0	0	0	2

For dose levels 5, 10 and 25 mg only one capsule of ACT-541468 is required, while for the 50 mg dose, two capsules of 25 mg will be administered. Therefore, to keep the blind, a placebo capsule matching ACT-541468 will be administered concomitantly with one capsule of ACT-541468 for the 5, 10 and 25 mg doses.

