1. Before study drug intake. 2. The hand-held device is handed out to the subject, in order to be completed for at least 7 consecutive days at home until V2 and at the site during visits. 3. Placebo single-blind treatment. 4. Includes AHI, PLMAI, SpO₂. 5. SAEs and AEs reporting and follow-up: all SAEs from signed ICF up to 30 days after double-blind study drug discontinuation. AEs from signed ICF up to 5 days after double-blind study drug discontinuation. 6. In case of permanent discontinuation, safety assessments of V7 are recommended to be performed within 24 hours of last study drug intake. 7. Approximately 30–60 minutes after PSG lights on [see Section 7.2 for the order of assessments]. 8. Telephone call. 9. Approximately 1 hour after lights on, if failed repeated every 30 minutes until subject safe to leave center [see Section 7.2 for the order of assessments]. 10. In the event of excessive sleepiness according to investigator opinion one hour after lights on in the morning after the first PSG night, it is recommended to draw a PK sample at this time. 11. Previous medications will be collected at V1.

AE, adverse event; AHI, Apnea/Hypopnea Index; C-SSRS[®], Columbia Suicide Severity Rating Scale; DSST[®], Digit Symbol Substitution Test; ECG, electrocardiogram; EOT, End of Treatment; follow-up; KSS, Karolinska Sleepiness Scale; ISI[®], Insomnia Severity Index; PK, pharmacokinetic; PLMAI, Periodic Limb Movement Arousal Index; PSG, polysomnography; SAE, serious adverse event; SDS[®], Sheehan Disability Scale; SpO₂, oxygen saturation by pulse oximetry; VAS, visual analog scale.

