7.2.4.8 Neurological examinations

In the morning following each PSG night (V2, V3, V4, V5, V6 and V7), a set of examinations must be performed approximately 1 hour after lights on [see Section 7.2]. The neurological examinations will be done by the investigator, a delegated physician, a specialist nurse or a nurse practitioner, trained according to local requirements and local clinical practice. The following examinations will be performed to detect a possible next-day residual effect :

- Gait
- Tandem walking
- Romberg test.

The set of examinations will be repeated approximately every 30 minutes until it is safe for the subject to leave the center [see Section 7.2]. The time when it is considered safe for the subject to leave the center will be recorded in the eCRF.

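### Gait, tandem-walking and Romberg results are listed but not counted by dose, and the time-to-leave summary is an insensitive substitute for a failure rate

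*SAP*

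**What the plan says.** Protocol 7.2.4.8 gives the examination a detection purpose: "The following examinations will be performed to detect a possible next-day residual effect". The tests are gait, tandem walking and Romberg. On timing, "a set of examinations must be performed approximately 1 hour after lights on", at V2 to V7, which is 6 visits × 2 mornings = 12 mornings per subject. On repetition, "The set of examinations will be repeated approximately every 30 minutes until it is safe for the subject to leave the center". Footnote 9 to Protocol Table 3 makes failure the trigger: "Approximately 1 hour after lights on, if failed repeated every 30 minutes until subject safe to leave center".

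SAP 10.5.4 is the only SAP section on this examination. It plans two summaries per scheduled morning, by dose group including single-blind placebo, by gender and overall:

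- the number (%) answering yes to "Is excessive sleepiness observed one hour after lights on";
- a duration: "The time from treatment until the subject is considered safe to leave the center the next day will be summarized".

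SAP section 4 defines a continuous summary as N, mean, SD, median, minimum and maximum. SAP section 10 has every safety item listed. Neither document plans a by-dose count of abnormal examinations, abnormal components or repeats. The exposure-safety plots in SAP 10.7 do not use the examination either.

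**The concern.** Protocol 1.3.1 says the dose for later trials will rest on WASO and on "safety data, such as next-day residual effect from baseline versus placebo". Protocol 1.1.4 builds the unmet need partly on postural instability and falls. Protocol 1.3.2 counts discharge after a neurological examination among the reasons why 50 mg can be tested, the highest evening dose in healthy elderly subjects so far being 25 mg.

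This examination is the only planned next-day measure aimed at gait and balance. DSST, KSS, SDS and the visual analog scales measure attention, hand speed, sleepiness and perceived function. The sleepiness question is not a motor result.

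At stake is whether someone comparing the doses can see how many subjects failed the balance tests at each dose. As the SAP stands, they would have to count from listings or infer it from a duration that barely responds.

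**Working it through.** **The plan's own figures.** The documents give no figure for this examination. The sample-size section (Protocol 10.5) supplies the number per dose: 50 subjects with 8% unavailable, so 50 × 0.92 = 46. As a check that 46 is what the plan used, the stated power was simulated (maximum effect 25 min, SD 40 min, correlation 0, two-sided 5%, the four candidate shapes). Power was 92.0%, 90.2%, 89.4% and 89.5%, average 90.3%, against the stated 89–92% and 90%.

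**Nominal time of the first examination**

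- Dose to lights off: the capsules "will be taken approximately 30 minutes before lights off" (Protocol 5.1.2.2), so about 30 min.
- Time in bed: 480 min (Protocol 6.1.1).
- Lights on to first examination: about 60 min (Protocol 7.2.4.8).
- Sum: 30 + 480 + 60 = 570 min, or 9.5 h after dosing.

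**Shift in the mean.** Assume a share p of subjects fails once and passes at the first repeat, about 30 min later. The shift is 30 × p, or 0.3 min per percentage point.

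| p | Shift in mean (min) |
|---|---|
| 1 of 46 | 30/46 = 0.65 |
| 5% | 1.5 |
| 10% | 3 |
| 20% | 6 |
| 30% | 9 |

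At 10% the change is 3/570 = 0.5%.

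**Shift against noise.** The documents give no SD for time to leave, so a routine SD of 10 to 30 min is assumed. The standard error of a dose mean is sqrt(SD² + 900·p(1−p)) / sqrt(46). At p = 10%:

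- SD 10: sqrt(100 + 81)/6.78 = 2.0 min
- SD 30: sqrt(900 + 81)/6.78 = 4.6 min

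The 3-minute shift is thus about the size of its own standard error. As a gauge only, since the SAP plans no test here, a simulated paired comparison of 10% failing against 0% on placebo has 7–21% power over this SD range. At 20% failing it has 15–59%.

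**The other planned statistics.** Simulated averages for 46 subjects, 0% against 10% failing:

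| Routine SD (min) | Median | SD | Maximum |
|---|---|---|---|
| 5 | 570.0 → 570.7 | 5.0 → 10.2 | 581.1 → 605.1 |
| 10 | 570.0 → 571.4 | 10.0 → 13.3 | 592.2 → 610.4 |
| 20 | 570.0 → 572.4 | 19.9 → 21.8 | 614.3 → 624.8 |
| 30 | 570.0 → 572.7 | 29.8 → 31.1 | 636.6 → 643.7 |

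With small spread the SD and maximum react clearly. With SD 20–30 the maximum moves by only about 7–11 min, which is hard to tell from routine delay. The maximum also does not count subjects: one failure and five failures can give the same value. No time statistic shows which test was failed.

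**What a count would show.** With 46 subjects:

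| True failure rate | P(at least 1 failure) | P(at least 3) |
|---|---|---|
| 5% | 91% | 41% |
| 10% | 99% | 85% |
| 20% | >99.9% | 99.7% |

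These are chances that failures appear in the table. They are not the power of a test, so they should not be set against the paired-comparison figures as like for like.

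**The case against.** The strongest defence is that the SAP drops nothing the protocol promised. The examination is absent from the safety endpoints in Protocol 6.2 and from the planned analyses in Protocol 10.3.5.6. Protocol 1.4.2 and 7.2.3.1 use it to decide whether a subject may leave, and time to leave summarizes that decision. SAP 10.5.4 already goes beyond the protocol's analysis section. This stands: the point is an improvement, not the repair of a lost endpoint. It does not answer the detection purpose in Protocol 7.2.4.8.

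A reader might go further and infer that the results go largely unreported, or are visible only in listings. The documents do not support that. Abnormal assessments that are clinically significant count as adverse events (Protocol 9.1.1), and these are summarized by dose. Excessive sleepiness, from the same eCRF page, is tabulated by dose. The adverse-event route is partial, though: a failed tandem walk that is passed 30 minutes later need not be judged clinically significant.

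A reader might also infer that a dose impairing balance would leave no trace in the time-to-leave table. That is too strong as well. The SAP gives SD, minimum and maximum besides mean and median, and with a routine SD of 5 min the maximum rises by 24 min at 10% failing. What is missing is a signal that is reliable and can be counted.

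Last, capture of each component and each repeat is not explicit. Protocol 7.2 sends assessments to the eCRF unless otherwise specified, and SAP 10.5.4 refers to a dedicated page for this examination, so capture is likely. But Protocol 7.2.4.8 names only the safe-to-leave time as recorded, and neither document defines an abnormal result for each test. This limits how detailed the table can be, not whether to have one.

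**Conclusion.** The concern holds in limited form. Gait, tandem-walking and Romberg results are listed but not counted by dose, and failures enter a by-dose table only as clinically significant adverse events. The duration summarized in their place moves its mean by 0.3 min per percentage point of subjects failing once, from about 570 min. Its SD and maximum are informative only when routine spread is small.

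This is a cheap and worthwhile improvement to a dose-response study whose dose choice uses next-day residual effect. It does not touch the primary analysis.

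The absence of a by-dose count is read directly from the documents. The sizes rest on assumptions: the failure rates, one 30-minute repeat per failure, a routine SD of 5–30 min, and 46 evaluable subjects per dose. The protocol's examination times are themselves approximate.

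**What to change.** Add to SAP 10.5.4, on the Safety Set, for each scheduled morning and dose group including single-blind placebo:

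- number (%) of subjects with an abnormal first examination, overall and separately for gait, tandem walking and Romberg where the eCRF captures the component;
- number (%) of subjects needing at least one repeat examination.

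Keep the sleepiness table and the time-to-leave summary. Before finalizing the wording, check the eCRF page to see which items are coded, and state in the SAP which recorded response counts as abnormal. If components are not coded, report the overall and repeat counts alone.

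The cost is a few lines of SAP text and one more descriptive table. No trial procedure, discharge decision or hypothesis test changes.

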### **10.5.5 Columbia Suicide Severity Rating Scale**

The Columbia Suicide Severity Rating Scale® (C-SSRS) is an instrument that evaluates suicidal ideation and behaviors.

The C-SSRS outcome categories are provided below. Each category has a binary response (yes/no) and are numbered and ordered below for convenience.

- 1 – Wish to be Dead
- 2 – Non-specific Active Suicidal Thoughts
- 3 – Active Suicidal Ideation with Any Methods (Not Plan) without Intent to Act
- 4 – Active Suicidal Ideation with Some Intent to Act, without Specific Plan
- 5 – Active Suicidal Ideation with Specific Plan and Intent
- 6 – Preparatory Acts or Behavior
- 7 – Aborted Attempt

- 8 – Interrupted Attempt
- 9 – Actual Attempt (non-fatal)
- 10 – Completed Suicide

Self-injurious behavior without suicidal intent is also a C-SSRS outcome (although not suicide-related) and has a binary response (yes/no).

Categories 1–5 relate to suicidal ideation and a score of 0 is assigned if no suicidal ideation is present. Categories 6–10 relate to suicidal behavior.

Number (%) of subjects with suicidal ideation, suicidal behavior, and/or self-injurious behavior without suicidal intent based on the C-SSRS during double-blind treatment will be tabulated. Percentages will be based on the number of subjects with at least one post-baseline C-SSRS assessment.

Shifts from baseline showing any changes in suicidal ideation and suicidal behavior in each treatment period will also be provided. Subjects will be summarized under the worst of the following three categories, shown here in the order from best to worst: 1) No suicidal ideation or behavior, 2) Suicidal ideation only, and 3) Suicidal ideation and behavior. Suicidal ideation includes any one of the five suicidal ideation events (categories 1–5). Suicidal behavior includes any one of the five suicidal behavior events (categories 6–10).

## 10.6 Pharmacokinetic

PK analyses will be performed based on the PK set.

Descriptive statistics (n, mean, standard deviation, CV%, m [number of non-zero concentrations], geometric mean, geometric standard deviation, geometric CV%, median, minimum and maximum) of ACT-541468 plasma concentration collected approximately 9–10 h post-dose in each treatment period (excluding double-blind placebo) will be provided for each time point (morning after the first and second PSG nights), by gender and overall. Note that the protocol recommends to draw a PK sample in the morning after the first PSG night only in subjects where excessive sleepiness is observed (according to investigator opinion) one hour after lights on.

Concentration values below the lower limit of quantification ( $< 1.0$  ng/mL) will be displayed in listings as zero with a flag and handled as zero in the calculations for mean, CV%, standard deviation, median, minimum, and maximum, but handled as missing for the calculation of the geometric mean, geometric standard deviation and geometric CV%.

All individual ACT-541468 plasma concentration data will be listed.

## 10.7 Exposure-safety analysis

The exposure-safety relationship will be explored using  $C_{9-10h}$  (plasma concentrations of ACT-541468 in the morning of the second PSG night in each treatment period [excluding

double-blind placebo]) and will be based on the PK set. Safety parameters considered for this analysis will include selected AEs (e.g., somnolence and/or excessive sleepiness), changes from baseline in DSST, KSS, SDS, and morning sleepiness (VAS for ‘the way you feel this morning’). C9-10h will be assessed against each safety parameter using graphical presentations.

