2.3 Other objectives

To explore the effect of ACT-541468 on other sleep parameters at each treatment period. Sleep parameters will include various objective and subjective measures [see [Appendix 10](#)].

To assess the safety and tolerability of oral administration ACT-541468 in elderly subjects with insomnia disorder.

To explore the relationship between exposure (concentration of ACT-541468 approximately 9–10 h post-dose at second morning of V3, V4, V5, V6, and V7) and safety.

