7.2.6 Pharmacokinetic assessments

PK samples will be collected in the morning after the second PSG night after lights on, approximately 9–10 hours post-dose at V3, V4, V5, V6 and V7. In the event of excessive sleepiness according to investigator opinion one hour after lights on in the morning after the first PSG night, it is also recommended to draw a PK sample at this time.

The date and the time of blood sample collection will be entered in the eCRF. The date and time of the last study treatment dosing before blood draw will be entered in the eCRF. The site staff will ship the plasma samples to the central laboratory, who will ship the samples to Actelion preclinical drug metabolism and pharmacokinetics department for the PK analysis.

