10.3.5.7 Exposure-safety analysis

The exposure-safety relationship will be explored using C_{9-10h} (plasma concentration of ACT-541468 the morning of the second PSG night at V3, V4, V5, V6 and V7) and will be based on the PK set. Safety parameters considered for this analysis will include selected AEs (e.g. somnolence), changes from baseline in DSST[®] and other parameters as relevant.

Further details will be provided in the SAP.

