## 2 STUDY DESIGN

This is a multi-center, double-blind, randomized, placebo-controlled, 5-period, 5-treatment crossover, polysomnography (PSG) dose-response Phase 2 study to assess the efficacy and safety of ACT-541468 in elderly subjects with insomnia disorder.

Approximately 50 subjects will be randomized in a 1:1:1:1:1 ratio to five different sequences of five study treatments according to a Latin square design as shown in [Table 1](#). The five study treatments are ACT-541468 5 mg (Dose 1), 10 mg (Dose 2), 25 mg (Dose 3), 50 mg (Dose 4), and placebo. In each treatment period, subjects are to receive one of five study treatments in the order of the sequence they are randomized to.

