#### **5.7 Pharmacokinetic analysis set**

The Pharmacokinetic analysis set (PK set) includes all subjects in the SS who have at least one PK sample collected after initiation of study drug.

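### The exposure-safety plots omit the double-blind placebo period and so have no randomised zero-exposure reference

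*SAP*

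**What the plan says.** **Objective.** Protocol 2.3 lists, among the other objectives, "To explore the relationship between exposure" and safety, with exposure taken as the concentration on the second morning of V3 to V7. SAP 3.3 repeats the objective.

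**Analysis in the protocol.** Protocol 10.3.5.7 defines the exposure variable as "plasma concentration of ACT-541468 the morning of the second PSG night at V3, V4, V5, V6 and V7". It names no excluded period and leaves further detail to the SAP.

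**Analysis in the SAP.** SAP 10.7 uses the same second-morning concentration in each treatment period, but its bracket excludes "double-blind placebo]) and will be based on the PK set". The safety parameters are selected adverse events and the changes in DSST, KSS, SDS and morning-sleepiness VAS. The method is graphical only: the concentration "will be assessed against each safety parameter using graphical presentations". No placebo points, reference line or band are specified.

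**Data collected.** Protocol 7.2.6 schedules the PK sample "approximately 9–10 hours post-dose at V3, V4, V5, V6 and V7", so one is also due in each subject's placebo period. The PK set (SAP 5.7) "includes all subjects in the SS who have at least one PK sample collected after initiation of study drug". It is a set of subjects and does not itself remove placebo periods.

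**The concern.** An exposure-response plot is read against the level expected with no drug. Every subject is due a randomised, double-blind placebo period in which the same scores and adverse events are recorded. Leaving that period out means the plots show only how outcomes vary among concentrations from 5 to 50 mg. If an effect were already present at the lowest concentrations, little gradient might remain to be seen, and a nearly flat plot could be taken as reassurance.

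This bears on a stated objective. Next-day residual effect is also the kind of safety information that Protocol 1.3.1 says will inform the dose for later trials, although that section does not refer to the exposure plots.

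**Working it through.** The documents give no figure for this analysis, so there is none to reproduce. The check is mainly a comparison of passages, with simple arithmetic.

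**1. How much is not plotted.** Inputs: "Approximately 50 subjects will be randomized in a 1:1:1:1:1 ratio" (SAP 2), five periods per subject, one of them placebo.
- All periods: 50 × 5 = 250 subject-periods.
- Active periods only: 50 × 4 = 200.
- Not plotted: 250 − 200 = 50, and 50/250 = 20%.
- If 8% of subjects were unavailable, the figure Protocol 10.5 assumes for WASO, then 50 × 0.92 = 46 subjects and 46 of 230 subject-periods are not plotted. The 8% is not an assumption about safety scores.

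**2. Whether zero is a fair concentration for the placebo period.** Inputs: half-life 9.9 h in elderly subjects and a washout of at least 5 days (Protocol 3.2).
- 5 × 24 = 120 h, and 120/9.9 = 12.1 half-lives.
- Residual fraction: 2^(−12.1) ≈ 0.0002, about 0.02%.
- SAP 10.6 already has values below 1.0 ng/mL "handled as zero in the calculations for mean, CV%, standard deviation, median, minimum, and maximum", so a numerical zero is in use.

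**3. What the run-in baseline can and cannot do.** SAP 10.5.1 to 10.5.3 measure DSST, KSS and SDS changes from the two run-in mornings at V2, and SAP 9 measures VAS changes from the V2 diary entries. Write the expected change at dose d in period p as

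 change = E(d) + s(p),

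where E is the drug effect and s the shift since V2 from order or practice. In the Latin square each treatment occurs once in every period. With equal sequences and complete data, the average shift S is therefore the same for every treatment:
- mean change on an active dose = E(d) + S
- mean change on placebo = S
- difference = E(d)

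An active-only plot shows E(d) + S and cannot separate the two terms. A mean change of zero at low concentration fits no effect with no practice gain. It also fits an impairment that a practice gain has cancelled. Protocol 3.2 acknowledges a possible order or learning effect and relies on averaging it over all treatments, placebo included. For DSST a practice effect is plausible: two mornings at each of six visits (V2 to V7) make 12 administrations, against eight test versions (Protocol 7.2.4.4), so at least 12 − 8 = 4 administrations reuse a version.

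**4. Adverse events.** These are not changes from a baseline. With active periods only, the plot has nothing against which to judge how often somnolence, for example, occurs without drug.

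**5. Illustration of hidden effect.** Assume that a safety effect followed one of the SAP's candidate shapes (SAP 7.3.1.1). The share of the 50 mg effect already present at 5 mg is

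 [5/(5 + ED50)] / [50/(50 + ED50)].

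| Shape | Share at 5 mg |
|---|---|
| Emax, ED50 1.11 | 0.818/0.978 = 84% |
| Emax, ED50 3.75 | 0.571/0.930 = 61% |
| Emax, ED50 15 | 0.250/0.769 = 32.5% |
| Linear | 5/50 = 10% |

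That share would not appear as a gradient among active doses. The shapes were set for WASO and for dose, not for safety or concentration, so the table shows what could happen and does not estimate harm.

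**The case against.** **A no-drug reference is already in most of the plots.** For the four scores, zero on the vertical axis is each subject's own value after placebo nights in the same sleep centre. A clear shift from zero at low concentration would be visible. This stands, and it rules out the claim that the plots cannot show any departure from no drug. It does not make the run-in equivalent to the randomised placebo period (step 3), and it does nothing for the adverse-event plots.

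**The placebo comparison is made elsewhere.** SAP 4 starts every by-dose summary with placebo, which covers adverse events, DSST, KSS, SDS and the VAS. This also stands. A reader might infer that the trial discards its placebo safety data or loses its basis for dose choice. The documents do not support that: no placebo observation leaves the by-dose safety summaries, and no section makes dose choice depend on the exposure plots. What the tables cannot do is relate an individual concentration to the no-drug level.

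**The bracket defines a concentration, not a plot layout.** The SAP does not forbid a placebo line. It does not call for one either, and a placebo-period observation has no concentration under the definition as written. Protocol 10.3.5.7 leaves detail to the SAP, so the exclusion can be read as a detail. It is nonetheless a narrowing, and SAP 12.1 and 12.3 do not mention it.

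**No model is fitted.** Correct. No gain in slope precision or power is claimed here.

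**Conclusion.** The point holds in a limited form. As written, the exposure-safety plots have no randomised zero-exposure reference. For DSST, KSS, SDS and morning sleepiness the run-in is a partial substitute, confounded with order or learning. For selected adverse events there is no reference in the plot.

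The size is one subject-period in five, about 50 of 250, not plotted in an exploratory, graphical analysis. The conclusion rests on reading the SAP 10.7 bracket as governing what is plotted, on all four scores being plotted as changes from V2, and on placebo-period exposure being effectively zero, which the protocol's half-life and washout support. How large any order effect is cannot be determined from the documents. Severity is minor.

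**What to change.** In SAP 10.7, plot the double-blind placebo-period observations of PK-set subjects at concentration zero with a distinct marker. Alternatively, overlay the placebo mean change with its 95% CI on the score plots and the placebo proportion on the adverse-event plots. Flag any placebo-period sample with a measurable concentration rather than setting it to zero without comment.

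Keep the placebo exclusion in SAP 10.6, where it belongs with the summaries of drug concentration. If the sponsor prefers to keep it in SAP 10.7 as well, state this and the reason in SAP section 12.

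The cost is a small programming change. The scores and adverse events are already collected, and no other analysis is affected.
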